10.2.3 Reporting of Abnormal LFTs

If a subject is noted to have ALT or AST elevated $>3 \times \text{ULN}$ on 2 consecutive occasions, the abnormality should be recorded as an AE. In addition, an LFT Increases page of the eCRF must be completed providing additional information on relevant recent history, risk factors, clinical signs and symptoms, and results of any additional diagnostic tests performed.

If a subject is noted to have ALT or AST $>3 \times \text{ULN}$ and total bilirubin $>2 \times \text{ULN}$ for which an alternative etiology has not been identified, the event should be recorded as an SAE and reported as per Section 10.2.2. The investigator must contact the Medical Monitor for discussion of the relevant subject details and possible alternative etiologies, such as acute viral hepatitis A or B or other acute liver disease or medical history/concurrent medical conditions. Follow-up laboratory tests as described in Section 9.1.8 must also be performed. In addition, an LFT Increases page of the eCRF must be completed and transmitted with the Takeda SAE form (as per Section 10.2.2).

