6.3 Premature Termination or Suspension of Study or Investigational Site

6.3.1 Criteria for Premature Termination or Suspension of the Study

The study will be completed as planned unless 1 or more of the following criteria are satisfied that require temporary suspension or early termination of the study:

- New information or other evaluation regarding the safety or efficacy of the study drug that indicates a change in the known risk/benefit profile for TAK-831, such that the risk is no longer acceptable for subjects participating in the study.
- Significant violation of Good Clinical Practice (GCP) that compromises the ability to achieve the primary study objectives or compromises subject safety.
- Two or more subjects experience an SAE.*
- Two or more subjects experience alanine aminotransferase (ALT) and/or aspartate aminotransferase (AST) elevations >5 times the upper limit of normal (ULN) in the absence of a concomitant bilirubin increase.*
- One or more subjects experience ALT and/or AST elevations $>3 \times ULN$ in the presence of a total bilirubin increase $>2 \times ULN$ or an international normalized ratio (INR) >1.5 without findings of cholestasis or other alternate etiology to explain the elevations (ie, “Hy’s Law cases”).

- Two or more subjects experience ALT and/or AST elevations $>3\times$ ULN with the appearance of fatigue, nausea, vomiting, right upper quadrant pain or tenderness, fever, rash, and/or eosinophilia ($>5\%$).*

* Please note that the study may be terminated early prior to full attainment of these criteria (eg, if just 1 subject experiences 1 of these events) if warranted by safety data from the other subjects dosed in the study to date.

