7.5 Criteria for Discontinuation or Withdrawal of a Subject

The primary reason for discontinuation or withdrawal of the subject from the study or study drug should be recorded in the eCRF using the following categories. For screen failure subjects, refer to [Section 9.1.17](#).

1. Pretreatment event (PTE) or AE. The subject has experienced a PTE or AE that requires early termination because continued participation imposes an unacceptable risk to the subject's health or the subject is unwilling to continue because of the PTE or AE.

- Liver Function Test (LFT) Abnormalities

Study drug should be discontinued immediately with appropriate clinical follow-up (including repeat laboratory tests, until a subject's laboratory profile has returned to normal/baseline status, see [Section 9.1.8](#)), if the following circumstances occur at any time during study drug treatment:

- ALT or AST $>8 \times$ ULN, or
- ALT or AST $>5 \times$ ULN and persists for >2 weeks or based on clinical judgment of the investigator, or

- ALT or AST $>3\times$ ULN in conjunction with elevated total bilirubin $>2\times$ ULN or INR >1.5 , or
 - ALT or AST $>3\times$ ULN with appearance of fatigue, nausea, vomiting, right upper quadrant pain or tenderness, fever, rash, and/or eosinophilia ($>5\%$).
2. Significant protocol deviation. The discovery postrandomization that the subject failed to meet protocol entry criteria or did not adhere to protocol requirements, and continued participation poses an unacceptable risk to the subject's health.
 3. Lost to follow-up. The subject did not return to the clinic and attempts to contact the subject were unsuccessful. Attempts to contact the subject must be documented in the subject's source documentation.
 4. Voluntary withdrawal. The subject (or subject's legally acceptable representative) wishes to withdraw from the study. The reason for withdrawal, if provided, should be recorded in the eCRF.

Note: All attempts should be made to determine the underlying reason for the withdrawal and, where possible, the primary underlying reason should be recorded (ie, withdrawal because of an AE should not be recorded in the "voluntary withdrawal" category).

5. Study termination. The sponsor, IRB, or regulatory agency terminates the study.
6. Pregnancy. The subject is found to be pregnant.
Note: If the subject is found to be pregnant, the subject must be withdrawn immediately. The procedure is described in Section 9.1.10.

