9.1.8 Procedures for Clinical Laboratory Samples

All samples will be collected in accordance with acceptable laboratory procedures. Laboratory samples will be collected following an overnight fast of ≥ 10 hours (except for those collected at Screening) on the days stipulated in the Schedule of Study Procedures in [Appendix A](#).

The tests that will be performed for each clinical laboratory specimen are listed in [Table 9.a](#).

Table 9.a Clinical Laboratory Tests

Hematology	Serum Chemistry	Urinalysis
RBCs	ALT	pH
WBCs with differential (% and absolute)	Albumin	Specific gravity
Hemoglobin	Alkaline phosphatase	Protein
Hematocrit	AST	Glucose
Platelets	Total bilirubin	Blood
Prothrombin time/INR	Direct bilirubin	Nitrite
aPTT	Total protein	
	Creatinine	Microscopic Analysis: (a)
	Blood urea nitrogen	RBC/high power field
	Creatine kinase	WBC/high power field
	GGT	Epithelial cells, casts, etc
	Potassium	
	Sodium	
	Glucose	
	Chloride	
	Bicarbonate	
	Calcium	

Diagnostic Screening:

Serum

HIV (b)
 HBsAg and anti-HCV (b)
Female subjects only:
 hCG (for pregnancy) (d)
 FSH (b) (e)

Urine

Drug screen including amphetamines, barbiturates, benzodiazepines, cannabinoids, cocaine, opiates, alcohol, and cotinine (c)

aPTT=activated partial thromboplastin time, FSH=follicle-stimulating hormone, GGT= γ -glutamyl transferase, hCG=human chorionic gonadotropin, RBC=red blood cell, WBC=white blood cell.

- (a) Microscopic examination of sediment to be performed only if the dipstick results are positive.
- (b) To be performed at Screening only.
- (c) To be performed at Screening and Check-in (Day -1) of Periods 1 and 2.
- (d) To be performed at Screening, Check-in (Day -1) of Period 1, and Study Exit/Early Termination.
- (e) For female subjects when menopause is suspected and subject is not surgically sterile.

The local laboratory will perform laboratory tests for hematology, serum chemistry, and urinalysis. The results of laboratory tests will be returned to the investigator, who is responsible for reviewing and filing these results.

If subjects experience ALT or AST $>3\times$ ULN, follow-up laboratory tests (at a minimum, serum alkaline phosphatase, ALT, AST, total bilirubin, GGT, and INR) should be performed preferably within 48 to 72 hours and no later than 7 days after the abnormality was noted (please refer to Section 7.5 for discontinuation criteria and Section 10.2.3 for reporting requirements related to abnormal LFT results).

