If the ALT or AST remains elevated $>3\times$ ULN on these 2 consecutive occasions, the investigator must contact the Medical Monitor for consideration of additional testing, close monitoring, possible discontinuation of study drug, discussion of the relevant subject details and possible alternative etiologies. The abnormality should be recorded as an AE (please refer to Section 10.2.3 for reporting requirements related to abnormal LFT results).

The investigator or designee is responsible for transcribing or attaching laboratory results to the eCRF. The investigator will maintain a copy of the laboratory accreditation and the reference ranges for the laboratory used.

Laboratory reports must be signed and dated by the principal investigator indicating that the report has been reviewed and any abnormalities have been assessed for clinical significance. Any abnormalities identified prior to the first dose of study drug will require clear and complete documentation in the source documents as to the investigator's assessment of not clinically significant before proceeding with enrollment or randomization.

All clinically significant laboratory abnormalities must be recorded as a PTE/AE in the subject's source documents and on the appropriate eCRF. A clinically significant laboratory abnormality that has been verified by retesting will be followed until the abnormality returns to an acceptable level or a satisfactory explanation has been obtained.

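### The automatic SAE rule for liver cases in Section 10.2.3 covers only the bilirubin branch of the protocol's one-subject Hy's Law criterion and leaves out INR >1.5 (minor)

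*Protocol*

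**What the plan says.** **Study-level rule (Protocol 6.3.1).** The criterion opens with "One or more subjects experience ALT and/or AST elevations" above 3×ULN. It is met when total bilirubin also exceeds 2×ULN "or an international normalized ratio (INR) >1.5 without findings of cholestasis or other alternate etiology to explain the elevations". The protocol labels both branches Hy's Law cases.

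**Subject-level rule (Protocol 7.5).** Study drug stops when ALT or AST exceeds 3×ULN and total bilirubin is above 2× "ULN or INR >1.5". There is no alternative-etiology condition here.

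**Reporting rule (Protocol 10.2.3).** When ALT or AST exceeds 3×ULN, total bilirubin exceeds 2×ULN and no other cause has been found, the case becomes an SAE by rule ("for which an alternative etiology has not been identified, the event should be recorded as an SAE and reported as per Section 10.2.2"). Section 10.2.2 then sets a 24-hour limit. The same paragraph requires Medical Monitor contact, follow-up laboratory tests and the LFT Increases page. INR is not mentioned anywhere in 10.2.3.

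**Retest rule (Protocol 9.1.8).** Any ALT or AST above 3×ULN leads to repeat tests, INR among them, which "should be performed preferably within 48 to 72 hours and no later than 7 days after the abnormality was noted". If the enzyme is still above 3×ULN "on these 2 consecutive occasions, the investigator must contact the Medical Monitor", whatever the bilirubin or INR.

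**The concern.** A reporting rule should reach at least every case that the stopping rule treats as decisive. Here the stopping rule has two branches and the automatic reporting rule has one. A site that follows 10.2.3 to the letter could hold a case that on its own meets a study suspension criterion, yet have no fixed time by which the sponsor must be told.

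The sponsor's own duties depend on that notice. Under 6.3.3 the sponsor supplies the procedure for suspension or termination. Under 10.3.1 the expedited reporting clocks start when the sponsor becomes aware. Section 11.0 provides for no data safety monitoring committee, so nobody else is placed to pick the case up.

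**Working it through.** No sample size, power or error rate is involved. The check is a comparison of the liver rules.

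| Protocol section | Level | Required alongside ALT/AST >3×ULN | Unexplained cases only? | Consequence |
|---|---|---|---|---|
| 6.3.1 | Study (1 subject suffices) | Bilirubin >2×ULN **or INR >1.5** | Yes | Suspension or termination |
| 7.5 | Subject | Bilirubin >2×ULN **or INR >1.5** | No | Study drug stopped |
| 10.2.3, second paragraph | Subject | Bilirubin >2×ULN | Yes | SAE by rule, 24-hour report, Medical Monitor contact on the first qualifying value |
| 10.2.3, first paragraph | Subject | A second consecutive value >3×ULN | No | AE record, LFT Increases page |
| 9.1.8 | Subject | A second consecutive value >3×ULN | No | Medical Monitor contact, AE record |

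**Step 1: can the INR branch be detected?** Yes. Table 9.a lists "Prothrombin time/INR" in the routine hematology panel. Appendix A and SAP 7.12.2 schedule clinical laboratory draws at Screening (1), Day -1 (2), Day 3 (2) and Study Exit (1): 1 + 2 + 2 + 1 = 6. At 21 mL each, 6 × 21 = 126 mL, which agrees with Table 9.f. Four of the six are postdose (Study Days 3, 8, 11 and 16), so INR is available each time the enzymes are.

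**Step 2: follow one case through the rules.** Take a subject with ALT or AST >3×ULN, INR >1.5, bilirubin at or below 2×ULN and no other cause.

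- 6.3.1: met.
- 7.5: met.
- 10.2.3, second paragraph: not met, because bilirubin is not above 2×ULN.
- 9.1.8: Medical Monitor contact becomes mandatory only if the repeat is also >3×ULN. If the repeat is lower, this rule never requires the call.

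**Step 3: do the general rules supply a deadline?**

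- 10.1.4 allows SAE status as an important medical event, but on the investigator's judgement. Table 10.a lists acute liver failure and hepatic necrosis. Its note treats the listed terms as broad concepts, so the case can be considered under them but is not placed there automatically.
- 9.1.8 has clinically significant laboratory abnormalities recorded as adverse events, with no time limit for telling the sponsor.
- Appendix B item 12 asks for prompt reporting of adverse reactions and gives 24 hours only for SAEs.

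**Result.** The automatic rule names 1 of the 2 branches of the one-subject criterion. No other rule gives the INR branch a mandatory 24-hour report.

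**The case against.** The strongest reply is that the omission would seldom change what happens. The affected subject is protected by 7.5, and exclusion 23 bars ALT/AST >1.5×ULN at the Period 2 Check-in. There is one site, its principal investigator signs every laboratory report, and 6.3.1 itself names INR >1.5. For harm to follow, that investigator would have to see a study-stopping result and not tell the sponsor. Section 4.1 reports no SAEs and no concerning laboratory trends in the two earlier studies, with single doses up to 750 mg. All of this stands, and it keeps the point minor. It does not make the two sections agree.

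Three stronger readings are tempting, and the documents do not support them.

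- *Medical Monitor contact is required only for the bilirubin branch.* Section 9.1.8 requires it for any ALT/AST >3×ULN on two consecutive occasions. What the INR branch lacks is a trigger at the first value.
- *The sponsor would hear too late, after other subjects' second dose.* This could happen but cannot be shown. Section 9.1.8 sets no minimum interval, so the repeat may come early, and subjects' dosing dates are not given. The 24-hour SAE limit counted from a Study Day 8 result itself runs into Study Day 9, the dosing day, so even the bilirubin branch has no assured notice before that dose.
- *Section 7.5 is a second Hy's Law criterion.* It shares the thresholds, but it is an individual stopping rule without the alternative-etiology condition.

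**Conclusion.** The inconsistency is real and rests on the text alone. An unexplained INR-branch case with bilirubin at or below 2×ULN meets the one-subject criterion in 6.3.1, yet has no automatic SAE status, no mandatory 24-hour report and no Medical Monitor contact required at the first value.

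The severity is minor. The likelihood is low, the subject-level protections hold, and the primary PK objective and its analysis are untouched. Confidence is high for the omission. The effect on the timing of sponsor notice cannot be quantified. The conclusion assumes that 10.2.3 is applied as written and that the investigator does not independently class the case as an important medical event.

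**What to change.** In the second paragraph of Protocol 10.2.3, add INR >1.5 as an alternative to the bilirubin threshold. The trigger becomes ALT or AST >3×ULN and (total bilirubin >2×ULN or INR >1.5). Keep the alternative-etiology condition and apply it to both branches. Leave the rest of the paragraph unchanged: the SAE report, Medical Monitor contact, follow-up tests and LFT Increases page.

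The cost is one clause in an amendment and an occasional extra SAE report, with no new test or visit. Such a report would count toward the separate 6.3.1 criterion "Two or more subjects experience an SAE". With the etiology condition kept, however, the case would normally already meet the one-subject criterion, so the stopping rules are not materially widened.

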10.3 Follow-up of SAEs

If information is not available at the time of the first report becomes available at a later date, the investigator should complete a follow-up SAE form or provide other written documentation and fax it immediately within 24 hours of receipt. Copies of any relevant data from the hospital notes

(eg, ECGs, laboratory tests, discharge summary, postmortem results) should be sent to the addressee, if requested.

All SAEs should be followed up until resolution or permanent outcome of the event. The timelines and procedure for follow-up reports are the same as those for the initial report.

10.3.1 Safety Reporting to Investigators, IRBs, and Regulatory Authorities

The sponsor will be responsible for reporting all suspected unexpected serious adverse reactions (SUSARs) and any other applicable SAEs to regulatory authorities, investigators, and IRBs, as applicable. Relative to the first awareness of the event by/or further provision to the sponsor or sponsor's designee, SUSARs will be submitted to the regulatory authorities as an expedited report within 7 days for fatal and life-threatening events and 15 days for other serious events, unless otherwise required by national regulations. The sponsor will also prepare an expedited report for other safety issues where these might materially alter the current benefit-risk assessment of the study drug or that would be sufficient to consider changes in study drug administration or in the overall conduct of the trial. The study site also will forward a copy of all expedited reports to his or her IRB.

11.0 STUDY-SPECIFIC COMMITTEES

No steering committee, data safety monitoring committee, or clinical endpoint committee will be used in this study.

12.0 DATA HANDLING AND RECORDKEEPING

The full details of procedures for data handling will be documented in the Data Management Plan. AEs, PTEs, medical history, and concurrent medical conditions will be coded using the Medical Dictionary for Regulatory Activities (MedDRA). Drugs will be coded using the World Health Organization Drug Dictionary.

12.1 eCRFs

Completed eCRFs are required for each subject who signs an informed consent.

The sponsor or its designee will supply study sites with access to eCRFs. The sponsor will make arrangements to train appropriate site staff in the use of the eCRF. These forms are used to transmit the information collected in the performance of this study to the sponsor and regulatory authorities. The eCRFs must be completed in English. Data are transcribed directly onto eCRFs.

After completion of the entry process, computer logic checks will be run to identify items, such as inconsistent dates, missing data, and questionable values. Queries may be issued by Takeda personnel (or designees) and will be answered by the site.

The principal investigator must review the eCRFs for completeness and accuracy and must sign and date the appropriate eCRFs as indicated. Furthermore, the investigator must retain full responsibility for the accuracy and authenticity of all data entered on the eCRFs.

The eCRFs will be reviewed for completeness and acceptability at the study site during periodic visits by sponsor or its designee. The sponsor or its designee will be permitted to review the subject's medical and hospital records pertinent to the study to ensure accuracy of the eCRFs. The completed eCRFs are the sole property of the sponsor and should not be made available in any form to third parties, except for authorized representatives of appropriate governmental health or regulatory authorities, without written permission of the sponsor.

After lock of the clinical study database or submission of the eCRFs to the sponsor, any change of, modification of, or addition to the data on eCRFs should be made by the investigator with use of change and modification records of eCRFs (Data Clarification Form) provided by the sponsor. The principal investigator must review the Data Clarification Form for completeness and accuracy, and must sign and date the form.

12.2 Record Retention

The investigator agrees to keep the records stipulated in Section 12.1 and those documents that include (but are not limited to) the study-specific documents, the identification log of all participating subjects, medical records, temporary media such as thermal sensitive paper, source worksheets, all original signed and dated informed consent forms, subject authorization forms regarding the use of personal health information (if separate from the informed consent forms), query responses/electronic copy of eCRFs, including the audit trail, and detailed records of drug disposition to enable evaluations or audits from regulatory authorities, the sponsor or its designees. Any source documentation printed on degradable thermal sensitive paper should be photocopied by the site and filed with the original in the subject's chart to ensure long-term legibility.

Furthermore, International Conference on Harmonisation (ICH) E6 Section 4.9.5 requires the investigator to retain essential documents specified in ICH E6 (Section 8) until at least 2 years after the last approval of a marketing application for a specified drug indication being investigated or, if an application is not approved, until at least 2 years after the investigation is discontinued and regulatory authorities are notified. In addition, ICH E6 Section 4.9.5 states that the study records should be retained until an amount of time specified by applicable regulatory requirements or for a time specified in the study site agreement between the investigator and sponsor.

Refer to the study site agreement for the sponsor's requirements on record retention. The investigator should contact and receive written approval from the sponsor before disposing of any such documents.

13.0 STATISTICAL METHODS

13.1 Statistical and Analytical Plans

A statistical analysis plan (SAP) will be prepared and finalized prior to database lock. This document will provide further details regarding the definition of analysis variables and analysis methodology to address all study objectives.

A targeted data review will be conducted prior to database lock. This review will assess the accuracy and completeness of the study database, subject evaluability, and appropriateness of the planned statistical methods.

13.1.1 Analysis Sets

Safety Analysis Set

The safety analysis set will consist of all enrolled subjects who received at least 1 dose of study drug. Subjects in this analysis set will be used for demographic, other baseline characteristic, and safety summaries.

PK Analysis Set

The PK analysis set will consist of subjects from the safety set who have at least 1 measurable postdose TAK-831 plasma concentration.

PD Analysis Set

CCI

If any subjects are found to have incomplete data, a decision will be made on a case-by-case basis as to their inclusion in the analysis; however, all data will be presented in the subject listings.

